Effect of the Temperature used in Thermal Radiofrequency Ablation on Outcomes of Lumbar Facets Medial Branches Denervation Procedures: A Randomized Double-Blinded Trial

[name], PhD; [name]; [name].

Protocol Version 3 Revision Date: 10/15/2019

Amendments to Protocol to-date:

• Amendment 1 Dated 24MAR2014:

"The protocol is being updated so that at the 12 month follow-up subjects who do not want to come to clinic can complete the questionnaire by mail or phone," has been added to the protocol.

• Amendment 2 Dated 14MAY2014:

"Change the last item in the exclusion criteria from: k. History of previous RFA at the same level(s) in the previous 12 months. To k. History of previous RFA at the same level(s) in the previous 6 months," has been changed on the current version of the protocol.

- Amendment 3 Dated 12NOV2014:
 "The investigator would like to add a window of +/- 1 week to the 1, 3, 6 and 12 month follow ups," has been disregarded therefore has not been added to the current protocol version.
- Amendment 4 Dated 23JAN2018: Change inclusion criteria f. to "f. Adequate response to the diagnostic block(s), 1 or more, at the same levels of the intended block (defined as ≥70% pain relief)." – which has been updated on current protocol version.
- Amendment 5 Dated 23JAN2018: Adjustment to the above stated amendment dated 24MAR2014 "The protocol is being updated so that subjects who do not want to come to clinic can complete the questionnaire by mail or phone for any of the follow-up visits". This has been added to the protocol.
- Amendment 6 Dated 23JAN2018: Spelling mistakes and references have been corrected.
- Amendment 7 Dated 23JAN2018: Page numbers have been added.
- Amendment 8 Dated 23JAN2018: Protocol version and revision date have been added.
- Amendment 9 Dated 15OCT2019 Protocol Version and revision date have been updated.

- Amendment 10 Dated 15OCT2019
 - Change exclusion criteria I to "i. Psychopathology including uncontrolled depression, somatization or poor coping skills."– Which has been updated on current protocol version.

Study Aims:

- 1. To compare the effects of 2 competing temperatures used for thermal Radiofrequency Ablation (RFA) of the lumbar facet medial branches in patients with chronic low back pain secondary to lumbar facets arthropathy.

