• Technique related data:

- The temperature of the probe used (80°C or 90°C)
- Duration of application of the RF probe is 90 seconds twice using 10mm active tip probe.
- Sensory stimulation 0.5mAmp
- Needle size 20G
- The number of ablated nerves.
- Side/Laterality.

• Outcomes Data:

Outcomes will be measured at baseline and 1, 3, 6 and 12 months follow-up visits post-procedure.

Primary outcomes:

Overall pain relief (i.e. percent of improvement) at each visit mentioned above.

Secondary outcomes:

- Postoperative Pain Scores in the subsequent visits using VAS at each visit mentioned above.
- Pain Questionnaires:
 - Pain Disability Index (PDI).
 - McGill Pain Questionnaire.
 - Beck Inventory (BI)
- Number of repeats of procedure in the first year after index procedure.

• Consumption of oral opioids in mg oral morphine equivalents recorded at the baseline before the procedure and then in the follow-ups post-procedure (1, 3, 6 and 12months).

- This table summarizes the morphine equivalent doses for the most commonly used morphine derivatives (7).

Drug Name	Oral dose equivalent to 30mg oral morphine sulfate	IV dose equivalent to 30mg oral morphine sulfate			
Morphine sulfate	30 mg (1:1 ratio)	10 mg (1:3)			
Hydromorphone	7.5 mg (1:4 ratio)	1.5 mg (1:20)			
Meperidine	300 mg(10:1 ratio)	100 mg (3.33:1)			
Methadone	12mg(1:2.5 ratio)	10 mg (1:3)			
Oxycodone	15 mg(1:2 ratio)	N/A			
Hydrocodone	30 mg(1:1 ratio)	N/A			
Codeine	200 mg(6.66:1 ratio)	120 mg (4:1)			

- The following formula will be used for Fentanyl transdermal patch:

- \circ 25 µg/h is equivalent to 87.5 mg morphine/24h
- \circ 50 µg/h is equivalent to 175 mg morphine/24h
- \circ 75 µg/h is equivalent to 262.5 mg morphine/24h
- \circ 100 µg/h is equivalent to 350 mg morphine/24h

• Adverse Events:

- Persistent paresthesia (yes/no)
- Nerve injury (yes/no)
- Infection (yes/no)
- Bleeding (yes/no)

• Data Analysis:

Standard descriptive statistics will be used to compare the randomized groups on baseline variables. Any obviously imbalanced co-variables (say, with a standardized difference greater than 0.20 in absolute value) will be adjusted for in both primary and secondary analyses. Our primary analysis will be intent-to-treat.

Primary Hypothesis:

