Graphically displayed over follow-up times (1, 3, 6 and 12 months) using boxplots containing the median, quartiles and outliers. At each follow-up time point (1,3, 6 and 12 months) we will assess whether 80°C and 90°C RFA temperatures differ with respect to the percentage of pain relief using the Wilcoxon rank-sum test. The significance criterion will be 0.05/4=0.0125 at each time, using a Bonferroni correction to control the type I error at 0.05 for the primary hypothesis. In addition to the P-value, the estimated median percentage of pain relief for each group and difference in medians with confidence intervals will be reported. The estimated probability of pain relief at 90°C being better than at 80°C with confidence interval will be reported, since the Wilcoxon rank sum test has a null hypothesis that this probability is 0.50. All the confidence intervals will be estimated based on bootstrapped standard error with 10,000 bootstrap replications (8).

Interim analyses:

Interim analyses will be conducted for efficacy and futility at each 25% of the maximum enrollment (see Sample Size Considerations) using a group sequential design and gamma spending function (using gamma = -4 for efficacy and -2 for futility). P-value boundaries for efficacy (futility in parentheses) will be P \leq 0.0016 (P>0.957), P \leq 0.0048 (P>0.719), P \leq 0.0147 (P>0.239), and P \leq 0.0440 (P>0.0040) at looks 1 through 4, respectively.

• Secondary hypotheses: We will compare randomized groups on the following variables:

VAS pain scores/Pain Disability Index (PDI)/McGill Pain questionnaire scores/Beck Inventory (BI) scores.

While the detailed description below focuses on the VAS pain score outcome for brevity, the analysis approach will be the same for Pain Disability Index (PDI), McGill Pain questionnaire scores, and Beck Inventory (BI) scores.

Graphical analysis will be undertaken to describe the degree of pain reduction observed in patients undergoing each treatment. The association between RFA temperature and pain reduction will be performed using a mixed effects model adjusting for time interval and also for baseline pain score to increase precision. We will assess the group-time interaction and assess treatment effects at each time if interaction P <0.15. The mixed model will account for potential intra-subject correlation of repeated VAS pain measurements within a patient using a spatial

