Sample size estimation is based on the frequency distribution estimated across four categories of pain relief used in our preliminary retrospective study. Thus, for these calculations 38%, 9%, 37%, and 16% of patients undergoing RFA at 80°C are assumed to develop no improvement (=0%), minimal improvement (<25%), moderate improvement (25-75%), and marked improvement (>75%) in symptoms, respectively. We further assumed that the data was uniformly distributed across each category through simulation, and performed power calculations on the simulated data using categories of percent pain relief of 0, 1-10, 11-20, 21-30, \dots , 91 – 100. In order to have 90% power at the 0.0125 significance level at each time point (0.05/4 = 0.0125 at each time point) to detect a clinically significant shift in improvement of absolute 15% between RFA at 90°C and RFA at 80°C, a maximum of N=216 total patients would be required. Below we list the proportion of patients in each percent pain relief category as assumed for the sample size calculations described above. Although a 20% increase is in general what would be considered a clinically important improvement in pain relief, we plan for 15% since there may be a nontrivial fraction of patients who experience no relief in either group. Adjusting for 3 interim analyses and a final analysis would require a maximum of N=237. With the above parameters, there will be a cumulative 8%, 37%, 75%, and 100% chance of crossing a boundary at the 1st through 4th analyses if the alternative hypothesis is true as stated above.

Group	0	1-10	11-20	21-30	31-40	41-50	51-60	61-70	71-80	81-90	91-100
Control	.38	.041	.035	.06	.07	.067	.069	.087	.062	.057	.072
Experimental	0	0	.399	.041	.03	.083	.068	.064	.077	.078	.16

We plan to re-estimate sample size after obtaining at least 1 and 3 month continuous pain relief outcome for the first 60 patients, using the observed shape of the distribution and the variability of the outcome, but still based on an absolute 15 percent upward shift from the 80 degrees group. Type I error will be controlled using the methods in Kieser 2000 (9).

We will provide results to the Data and Safety Committee on efficacy and safety assessments, including conditional power analyses, but the committee will have final say on whether the study would progress to the next interim analysis or be stopped.

References

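### Interim looks are triggered by enrolment, but the fixed P boundaries assume that 25/50/75% of patients already have the tested outcome, which makes futility too easy to cross, mainly at 12 months

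*Combined protocol and SAP*

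**What the plan says.** Under Interim analyses (Data Analysis), the trigger is enrolment: "Interim analyses will be conducted for efficacy and futility at each 25% of the maximum enrollment". The method is a group sequential design with a "gamma spending function (using gamma = -4 for efficacy and -2 for futility". One list of fixed P values follows: efficacy 0.0016, 0.0048, 0.0147 and 0.0440, and futility above 0.957, 0.719, 0.239 and (as printed) 0.0040.

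Under Outcomes Data, "Outcomes will be measured at baseline and 1, 3, 6 and 12 months follow-up visits post-procedure". Under Primary Hypothesis, each follow-up time has its own test of whether the groups "differ with respect to the percentage of pain relief using the Wilcoxon rank-sum test", and "The significance criterion will be 0.05/4=0.0125 at each time".

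Sample size considerations gives a fixed-design N of 216, a maximum of 237 after adjusting for the looks, and states that "there will be a cumulative 8%, 37%, 75%, and 100% chance of crossing a boundary at the 1st through 4th analyses" if the alternative is true. That section ties the sample size re-estimation to available 1- and 3-month outcomes in the first 60 patients. It also leaves the decision to continue or stop to the Data and Safety Committee.

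The plan does not say that patients counted at a look must have reached any visit, which of the four tests a look applies to, or that boundaries will be recomputed at the information observed.

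**The concern.** A group sequential boundary is valid for a given information fraction. For a visit L months after the procedure, the information at a look comes from patients who have reached that visit, not from all those enrolled. With an enrolment trigger, everyone enrolled in the last 12 months is missing from the 12-month test, and everyone enrolled in the last 6 months from the 6-month test.

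Futility boundaries tighten as information grows. A threshold meant for 75% information, applied at 25%, asks for a signal that a truly effective treatment often cannot yet show. At stake is a wrong futility signal on the 12-month comparison, one of four primary time points and the one that speaks to durability.

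**Working it through.** **Inputs from the plan.** Looks at 25/50/75/100% of enrolment; gamma −4 (efficacy) and −2 (futility); 90% power; N = 216 fixed and 237 maximum; the printed P values; visit lags of 1, 3, 6 and 12 months; the category table of pain relief.

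**Assumptions (not in the plan).** Even accrual over T years, no dropout, complete data at the final look, two-sided tests, printed interim boundaries acted on, final boundary 0.0440.

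**1. Reproduce the printed design.** Spending by information t:
- alpha(t) = 0.05(e^{4t} − 1)/(e^{4} − 1)
- beta(t) = 0.10(e^{2t} − 1)/(e^{2} − 1)

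At t = 0.25, alpha = 0.05 × 1.718/53.60 = 0.0016, the first printed efficacy value. Recursive integration at t = 0.25, 0.50, 0.75, 1 with non-binding futility gives:
- efficacy 0.0016/0.0048/0.0147/0.0440
- futility 0.957/0.719/0.239, then 0.044 at the last look
- inflation 1.0966, so 216 × 1.0966 = 236.9, i.e. 237
- cumulative crossing 8.3/37.3/75.2/100%

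Everything matches except the printed final futility value of 0.0040. Binding futility gives 0.0491 at the last look and N = 231, so it does not match. The planned chance of a futility crossing at looks 1–3 under the alternative is beta(0.75) = 0.10 × 3.482/6.389 = 5.45%.

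**2. Drift under the planned effect.** Two values are defensible.
- The printed design's own (alpha 0.05, power 90%): (1.960 + 1.282) × √1.0966 = 3.39.
- Implied by N = 237 and the category table, since N was sized at 0.0125. The table gives a probability of 0.648 that 90°C is better, with a tie factor of 0.979: √(3 × 237/0.979) × (0.6477 − 0.5) = 3.98.

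**3. Information actually available.** At look k, I = max(0, k/4 − L/(12T)).

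**4. Results for the 12-month test.** Futility means crossing at looks 1–3.

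| Accrual | Information at looks 1/2/3 | Futility, power (drift 3.39) | Futility, power (drift 3.98) | Two-sided type I |
|---|---|---|---|---|
| As designed | 25/50/75% | 5.5%, 90% | 2%, 97% | 0.050 |
| 6 years | 8/33/58% | 12%, 84% | 7%, 92% | 0.054 |
| 4 years | 0/25/50% | 15%, 82% | 8%, 91% | 0.054 |
| 3 years | 0/17/42% | 22%, 75% | 14%, 85% | 0.056 |
| 2 years | 0/0/25% | 30%, 67% | 21%, 78% | 0.055 |

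**Hand check of the last row.** The only interim with 12-month data is look 3, at I = 0.25, with boundary P > 0.239, i.e. |Z| < 1.177. The mean of Z is 3.39 × √0.25 = 1.697, so the chance is Φ(1.177 − 1.697) − Φ(−1.177 − 1.697) = 0.302 − 0.002 = 0.30. With drift 3.98 the mean is 1.989, and the chance is 0.208 − 0.001 = 0.21. The plan's futility spending function allows beta(0.25) = 0.10 × 0.649/6.389 = 1.0% at that information.

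**5. The 6-month test over the same 2 to 6 years.** Futility is 8–15% (power 82–88%) at drift 3.39, and 4–8% (power 91–95%) at drift 3.98. The low end is slow accrual.

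**6. Boundaries the named spending functions would give.** At 4 patients per month, 12-month information is 0.05/0.30/0.55, and futility would be P > 0.998/0.938/0.625, against the printed 0.957/0.719/0.239.

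**The case against.** **A crossing need not stop the trial.** The boundaries reproduce only as non-binding, and the committee receives conditional power analyses and has the final say. This stands: every percentage above is a chance of crossing. It does not make a boundary that is wrong for its data a sound guide.

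**Accrual is unknown.** This also stands. A reader might take the amendment dates, from March 2014 to "Amendment 10 Dated 15OCT2019", as showing enrolment of more than five years. They fix neither the start, the end nor the pace. Spreading 237 patients over that span (about 5.6 years) would give 12-month information of 7/32/57%, so the direction is unchanged. If accrual were so fast that look 3 came within 12 months of the first patient, there would be no 12-month interim data and no such test to stop.

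**Looks may be meant on fully followed 25% cohorts.** That is possible, and the printed figures would then be right, but the text does not say so. The plan ties its re-estimation to outcome data at about the same size (60 patients, against 237/4 = 59), so the difference in wording matters.

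**Stronger readings that do not hold.** A reader might infer that false futility far exceeds the planned 10% beta. At drift 3.98 and accrual over 4 to 6 years it does not: crossing is 7–8% and power 91–92%. Nor is the 6-month test generally starved of data, and a type I change from 0.050 to at most about 0.056 is not a material loss of control. The plan also does not say that a crossing at any single visit stops the trial. It names no driving visit, a gap that would exist without any lag.

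**Conclusion.** The point holds for the literal text: the trigger counts enrolled patients, while the boundaries count patients with outcomes. The consequence is lost power through premature futility crossings. It falls mainly on the 12-month test and is smaller at 6 months. Its size depends on an accrual rate that the plan does not give and on which drift is used, so the ranges should be carried rather than a single figure. That the printed boundaries assume equal 25% steps of outcome information is certain from the reproduction.

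Two neighbouring matters are separate and not counted here: the boundaries spend 0.05 in total although each visit is tested at 0.0125, and the last futility value looks like a misprint.

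**What to change.** In the Interim analyses section, do one of the following:
- define each look by the number of patients with the outcome at a named visit, for example 25/50/75% of the maximum with 12-month data; or
- keep the enrolment trigger, but replace the fixed P values with the gamma(−4)/gamma(−2) functions already named, evaluated for each visit at its observed information fraction (patients with that visit's outcome divided by the planned maximum).

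In either case, state which visit's test drives stopping.

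The cost is a few sentences in the plan and the committee's charter. Under the first option, looks come later. With even accrual, 75% have 12-month data at 0.75T + 1 years, which is at or after the end of enrolment whenever T is 4 years or less. Under the second, early stopping on later visits becomes less likely, and the boundaries must be recomputed at each look.

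### At the final look the futility threshold (P>0.0040) overlaps the efficacy threshold (P≤0.0440), so a P-value between them meets both rules

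*Combined protocol and SAP*

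**What the plan says.** The Interim analyses section plans looks for efficacy and futility at every quarter of maximum enrolment, with a "gamma spending function (using gamma = -4 for efficacy and -2 for futility"). It defines each pair of numbers by the words "P-value boundaries for efficacy (futility in parentheses) will be", so the first number is the efficacy cut-off and the one in brackets the futility cut-off. The pairs are 0.0016 (0.957), 0.0048 (0.719) and 0.0147 (0.239) at looks 1 to 3. The last pair is printed as "0.0440 (P>0.0040) at looks 1 through 4, respectively".

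Sample size considerations gives a fixed-design total of 216, a maximum of 237 after allowing for the interim looks, and cumulative boundary-crossing probabilities of 8%, 37%, 75% and 100% under the alternative. No other section gives a different final futility value or says which rule takes precedence.

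**The concern.** At looks 1 to 3 the futility cut-off lies well above the efficacy cut-off, and the gap between them is the region in which the trial continues. At look 4 there is no continuing, so the two cut-offs must coincide: every final P-value has to give exactly one conclusion. As printed, the order is reversed. A final P of 0.01, 0.02 or 0.04 is at or below 0.0440, so efficacy is declared; it is also above 0.0040, so futility is declared.

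Look 4 settles every trial that has not stopped early. With two opposite rules in force, the choice between them would have to be made with the P-value already known, which is what fixing the boundaries in advance is meant to prevent.

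**Working it through.** **Inputs from the plan**
- Looks at information fractions t = 0.25, 0.50, 0.75, 1.00: "Interim analyses will be conducted for efficacy and futility at each 25% of the maximum enrollment".
- Gamma family spending, -4 for efficacy and -2 for futility.
- Power 90%, so beta = 0.10: "In order to have 90% power at the 0.0125 significance level at each time point".
- Fixed-design N = 216 and maximum N = 237 (Sample size considerations).

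**Inputs inferred**
- Two-sided test. The plan does not say so, but the primary analysis asks whether the groups differ, and the printed values reproduce only on that basis.
- Total alpha 0.05. The printed efficacy boundaries reproduce at 0.05 and not at 0.0125.
- Symmetric inner-wedge futility bounds, with efficacy bounds computed as if futility were non-binding.

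**Step 1: spending.** Cumulative error spent at t is e × (1 − exp(−γt)) / (1 − exp(−γ)), where e is alpha or beta.
- Alpha, γ = −4: 0.0016, 0.0060, 0.0178, 0.0500.
- Beta, γ = −2: 0.010, 0.027, 0.054, 0.100.

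**Step 2: boundaries.** Recursive numerical integration gives the z-bounds. The drift (expected z at t = 1) is solved so that the two bounds meet at look 4; it is 3.3945.

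| Look | Efficacy z | Efficacy P | Printed | Futility z | Futility P | Printed |
|---|---|---|---|---|---|---|
| 1 | 3.155 | 0.0016 | 0.0016 | 0.054 | 0.957 | 0.957 |
| 2 | 2.818 | 0.0048 | 0.0048 | 0.360 | 0.719 | 0.719 |
| 3 | 2.439 | 0.0147 | 0.0147 | 1.178 | 0.239 | 0.239 |
| 4 | 2.014 | 0.0440 | 0.0440 | 2.014 | **0.0440** | **0.0040** |

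Hand check at look 1: z has mean 3.3945 × √0.25 = 1.697. Then P(|z| < 0.054) = Φ(−1.643) − Φ(−1.751) ≈ 0.050 − 0.040 = 0.010, the beta to be spent there.

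**Step 3: the plan's other figures.** The inflation factor is 1.0966, and 216 × 1.0966 = 236.9 (stated 237). Cumulative crossing under the alternative is 8.3%, 37.3%, 75.2% and 100% (stated 8, 37, 75, 100). Seven of the eight boundaries, the maximum N and the crossing probabilities thus come from one design, and only 0.0040 does not fit it. Variants with alpha 0.0125, a one-sided test, one-directional futility or beta 0.20 do not give 0.0040 either.

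**Step 4: size of the contradictory zone.** Interim futility stops are taken as followed. Two drifts are used:
- 3.3945 = (1.960 + 1.282) × √1.0966, which gives 90% power with the printed boundaries and matches the stated crossing probabilities.
- 3.958 = (2.498 + 1.282) × √1.0966, which is implied by sizing the trial at 0.0125.

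| Scenario | Reach look 4 | Reject, final bar 0.0440 | Reject, final bar 0.0040 | In the zone |
|---|---|---|---|---|
| Drift 3.3945 | 24.8% | 90.0% | 76.7% | 13.3% |
| Drift 3.958 | 14% | 96% | 90% | 6.8% |
| Null | 20% | 4.6% | 1.9% | 2.7% |

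The zone is the difference between the two rejection columns, for example 90.0 − 76.7 = 13.3. At drift 3.3945 that is 13.3 / 24.8 = 54% of the trials that reach look 4.

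**Step 5: the 0.0125 scale.** With the same spending functions at total alpha 0.0125, two-sided, both look-4 bounds are 0.0105. The conclusion that they must be equal does not depend on the alpha scale.

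**The case against.** The strongest reply is that this is one wrong digit and not a design choice. Everything around it points to 0.0440, the stated 100% crossing at look 4 fits bounds that meet, and a statistician rerunning the spending functions would recover the intended value. That is very likely right, though it remains an inference. The text examined here was extracted from a PDF, so a misread digit cannot be excluded until the printed page is checked. If the page does read 0.0040, a reader cannot tell a slip from a deliberately stricter bar without rebuilding the design.

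A second reply is that futility has no job at the last look, since nothing is left to stop, and the efficacy bound alone should decide. That is a sensible reading, but the plan prints a futility bound for look 4 and does not say it is to be ignored. The Data and Safety Committee's final say concerns whether the study goes on to the next analysis, not how the final P-value is read.

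A third is that the fall to 77% power is hypothetical. It arises only if 0.0040 is used as the bar, and on the 0.0125 sizing even that reading leaves about 90% power. Both points stand. Using 0.0040 is also conservative, so it would not raise the type I error.

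Finally, the plan also states "The significance criterion will be 0.05/4=0.0125 at each time", while the printed boundaries spend 0.05 in total. That conflict is separate and arguably larger. Correcting this digit does not resolve it.

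**Conclusion.** The concern holds. As printed, any final P with 0.0040 < P ≤ 0.0440 meets two opposite decision rules, and no section resolves this. The plan's own design gives 0.0440 for the final futility boundary.

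The share of trials affected is 13% under the alternative that matches the stated crossing probabilities, 6.8% under the larger effect implied by sizing at 0.0125, and 2.7% under the null. The overlap itself can be read off the page and needs no assumptions. The corrected value and these percentages rest on a two-sided test, inner-wedge futility, equally spaced looks and interim futility stops being followed. The first two are inferred, but they are supported by the match to the plan's other figures. Because the final decision threshold is involved, it must be corrected even if the cause is only a misprint.

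**What to change.** Check the look-4 futility value against the source document and the original design output. Then set it equal to the final efficacy threshold: P>0.0440 if the boundary set stays as printed at total alpha 0.05. On that route the cost is one number in the protocol.

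If the boundaries are instead brought into line with the 0.0125 criterion per time point, all eight must be recomputed, and the final pair becomes P≤0.0105 for efficacy and P>0.0105 for futility. That takes a rerun of the design software and a check of the maximum N. On either route, make the correction before any final analysis is seen.

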- 2. This prospective study will assess the relative effects of two temperatures (in degrees Celsius) used to ablate the targeted nerves in regards to pain management and possible complications.

Research Question:

Which temperature used to produce RF lesion (80°C or 90°C) is associated with better overall improvement in facet-mediated chronic low back pain?

Specific Hypotheses:

Primary

Lumbar facets medial branches RFA at 90°C provides more overall pain relief (i.e. percent of improvement), when compared to ablation at 80°C with no additional adverse events.

Secondary

Ablation of the lumbar facets nerve supply at 90°C will provide better improvement in the functionality level, general mood and quality of life as measured by VAS (Visual Analog Scale) pain score, Pain Disability Index (PDI), McGill Pain and Beck Inventory (BI) questionnaire scores than those receiving the ablation at 80°C. Furthermore, it is associated with less opioid consumption, no additional unwanted adverse events and/or complications along with less need to repeat RFA procedure over one year follow-up period.

Significance/Importance:

Chronic lower back pain (LBP) is a significant health care issue in the United States and the world. Chronic LBP contributes to decreased quality of life, decreased functionality and increased utilization of health care resources. The causes of chronic LBP tend to be multi-factorial. Arthropathy of the lumbar facet joints is thought to be a common etiology (15-45%) (1). Radiofrequency Ablation (RFA) of the medial branch nerve of the facet joint is a well-established treatment modality used to decrease facet joint pains. However, a wide range

Protocol Version 3 Revision Date: 10/15/2019 of temperature is being used (70-90 degrees Celsius). In addition, the optimal temperature that provides the best patient outcomes with the least side effects is not well established in the pain management literature.

Summary of Literature:

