correlation structure. A model-based Wald test for regression model coefficients will be used to evaluate whether or not RFA temperature affects mean pain reduction.

Opioid Consumption:

As preliminary retrospective study showed, postoperative opioid consumption is largely binary in nature for this patient's population, as over 60% of our patients did not take any opioids. Thus, postoperative opioid consumption within a year of the first RFA will be analyzed as a binary outcome, i.e., any versus none (however, dosage information among the subset of patients taking any opioids will be described using medians and quartiles for each group). Multivariable logistic regression will be used to estimate the adjusted relative risk for postoperative opioid use comparing patients undergoing RFA at 90°C to patients undergoing RFA at 80°C. A logistic model-based Wald test for regression coefficients will be used to test the hypothesis of the effect of temperature on the postoperative opioids use (i.e., whether or not the relative risk is different from a value of 1.0).

Number of repeat of RFA procedures

Need for repeated RFA procedure over one year period will be analyzed as a count variable using a proportional odds logistic regression model. If the number of repeats greater than 1 is very rare, we will use a binary outcome of any RFA procedure comparing two groups of patients.

Complications:

Incidence of each individual complication will be reported for each group, with confidence intervals. Possible adverse events (persistent paresthesia, nerve injury, bleeding and infection) will be summarized into a single composite binary outcome, i.e., any versus none. The risk of experiencing one or more adverse events will be compared between RFA at 90°C and RFA at 80°C groups using logistic regression.

Type I error will be controlled at 5% for the secondary outcomes using the Bonferroni correction for simultaneous hypotheses. SAS 9.3 software (SAS Institute, Cary, NC) and R statistical software version 2.7.2 (The R Foundation for Statistical Computing, Vienna, Austria) will be used for all analyses and graphics.

Sample size considerations:

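### The only tested opioid outcome, any use within a year of the procedure, does not register patients who stop opioids after the first follow-up visit

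*Combined protocol and SAP*

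**What the plan says.** All references are to the combined protocol and SAP.

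- Specific Hypotheses, Secondary: for ablation at 90°C, "it is associated with less opioid consumption".
- Outcomes Data, Secondary outcomes: "Consumption of oral opioids in mg oral morphine equivalents recorded at the baseline before the procedure and then in the follow-ups post-procedure", at 1, 3, 6 and 12 months. Patient Baseline data also lists the daily morphine-equivalent dose. No inclusion or exclusion criterion bars current opioid users.
- Data Analysis, Opioid Consumption: "postoperative opioid consumption within a year of the first RFA will be analyzed as a binary outcome, i.e., any versus none". The reason given is that use is largely binary, "as over 60% of our patients did not take any opioids". Dose is not tested; instead, "dosage information among the subset of patients taking any opioids will be described using medians and quartiles for each group". The test is a Wald test in a multivariable logistic model of "whether or not the relative risk is different from a value of 1.0".
- Data Analysis (opening paragraph): covariates are adjusted for if visibly imbalanced. Baseline opioid use is not named as a covariate.
- Secondary hypotheses: VAS, PDI, McGill and Beck scores, collected on the same visit schedule, get a mixed model adjusted for baseline and time, with a check of group-by-time interaction.

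The plan does not state how the four opioid records are combined. The literal reading, used here, is that use recorded at any follow-up visit counts.

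**The concern.** The window opens at the procedure and has no lead-in. Once a patient has been recorded as a user, nothing that happens later can change the outcome. If better pain relief lets patients come off opioids over several months, that benefit does not enter the only opioid comparison that is tested. The dose summary does not fill the gap: it is descriptive, and it is confined to users, a subset defined after randomisation.

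The stated reason does not cover this choice. A large share of non-users is a reason to dichotomise dose. It is not a reason to reduce four visits to one flag, because use or non-use at each visit is just as binary and keeps the timing.

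At stake is a null result on the flag being reported as no effect of temperature on opioids when the arms in fact differed in later discontinuation.

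**Working it through.** **The plan's own figure.** The documents give no power or sample size for opioids. The sample size they do give, 216 before interim looks, is for the primary Wilcoxon test, and it reproduces. From the table in Sample size considerations, P(90°C better) = 0.648. The Noether formula, N = (2.498 + 1.282)² / [3 × (0.648 − 0.5)²] with unrounded P, gives about 219, or 214 with the tie correction. Simulated power at 216 is 90.3%. The maximum of 237 at 1:1 gives 118 per group, used below with no dropout.

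**Assumed inputs.** None of these is in the documents.
- Baseline users b = 40%, with 30 to 50% as the range. The plan's figure of over 60% non-users describes postoperative use, so it is only a rough guide to baseline use.
- 5% of non-users start during the year and are still users at 12 months.
- Stopping among baseline users by 12 months is 25% at 80°C and 50% at 90°C, with no restarting.
- Stopping by month 1, s₁, is varied.

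**Formulas.**
- Flag: b(1 − s₁) + 0.05(1 − b).
- Use at 12 months: b(1 − s₁₂) + 0.05(1 − b).
- Power is the two-sided normal approximation for two proportions, with pooled variance under the null and unpooled under the alternative.

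**Results at b = 40%**, where starters contribute 0.05 × 0.60 = 3%:

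| Outcome | Stopping, 80°C v 90°C | Rates | RR | Power at 0.05 | Power at 0.05/7 |
|---|---|---|---|---|---|
| Flag | 5% v 5% by month 1 | 41% v 41% | 1.00 | 5% (alpha only) | 0.7% (alpha only) |
| Flag | 10% v 20% by month 1 | 39% v 35% | 0.90 | 10% | 2% |
| Flag | 10% v 30% by month 1 | 39% v 31% | 0.79 | 25% | 8% |
| Flag | 10% v 40% by month 1 | 39% v 27% | 0.69 | 50% | 23% |
| Use at 12 months | 25% v 50% by month 12 | 33% v 23% | 0.70 | 40% | 16% |

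Worked example, 12 months: 0.40 × 0.75 + 0.03 = 0.33 and 0.40 × 0.50 + 0.03 = 0.23. The null SE is √(2 × 0.28 × 0.72 / 118) = 0.0585 and the alternative SE is 0.0581. Power = Φ[(0.10 − 1.96 × 0.0585) / 0.0581] = Φ(−0.25) = 40%.

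The 0.05/7 column assumes that the plan's Bonferroni correction spans seven secondary tests: VAS, PDI, McGill, Beck, opioids, repeat procedures and complications. The plan does not state the number.

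**Range.** With 30 to 50% baseline users, the flag has 5 to 12% power at 0.05 in the first two scenarios. Use at 12 months has 28 to 53%.

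**The case against.** A reader might infer that the trial cannot show an opioid reduction at all, or that the flag merely reproduces baseline status. The documents support neither. With over 60% non-users in the retrospective data the flag is not saturated, and a smaller share of patients with any use is one form of lower consumption. At 118 per group, any use of 40% v 20% would be detected with 92% power at 0.05 (75% at 0.05/7). How closely the flag follows baseline status depends on stopping and starting rates that the documents do not give.

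The size of the problem also turns on timing. The relative risk of 1.00 follows directly from assuming equal stopping by month 1. The plan tests pain relief at month 1 and seeks 90% power at each time point, so it allows for an early effect. If stopping by month 1 were 10% v 40%, the flag would have 50% power, more than the 12-month comparison.

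Finally, the 12-month visit is not the only natural choice. It ignores use at months 1 to 6, and repeat ablation, which is itself hypothesised to differ by arm, may alter it.

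All of this stands, and it limits the claim to insensitivity. It does not answer the structural point: stopping after a first recorded use adds nothing to the tested contrast, and no other planned opioid analysis tests it.

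**Conclusion.** The point holds as a mismatch between hypothesis and test. The flag is insensitive to stopping after the first follow-up visit, although the data needed to see such stopping are collected. When the arms separate mainly after month 1, a doubling of 12-month discontinuation (25% v 50%) appears as a relative risk of 0.90 to 1.00 on the flag, against 0.70 for use at 12 months. These sizes rest on the assumed rates, full enrolment to 237 and no dropout.

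A reader might also infer that a later endpoint would make the opioid hypothesis well powered. It would not: about 40% at 0.05, and about 16% at the assumed 0.05/7. The gain is an estimate that addresses the hypothesis, and more sensitivity to late effects. This concerns one secondary outcome and leaves the primary analysis untouched. It is worth changing because the change is cheap.

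**What to change.** In Data Analysis, Opioid Consumption, replace the single flag by use or non-use at each of 1, 3, 6 and 12 months. Fit one repeated-measures binary model (GEE logistic or log-binomial) with group, visit and baseline opioid use, and assess group-by-visit as the plan already does for VAS. Name one contrast in advance as the test: either the average over visits, with the 12-month estimate reported beside it, or the 12-month contrast itself. Keep any use within the year as a descriptive line.

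The cost is SAP wording and slightly more modelling, with no new data. Patients with missed visits enter under a missing-at-random assumption, which should be stated. Use by visit still does not capture tapering among continuing users, and 12-month use may be affected by repeat ablation; both limits should be acknowledged. Power for the visit-averaged contrast depends on the within-patient correlation of use, which the documents do not give, and was not computed here.
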